
 To assess the improvement with EN3835 vs placebo in the FFI difficulty subscale in participants on the difficulty subscale at baseline. 	
 The difference between EN3835 and placebo in the mean change from Baseline (Day 1) to Day 57 on the difficulty subscale (total score on 9 items) of the FFI, ranging from 0 (“No Difficulty”) to 4 (“A Lot of Difficulty”). The mean change from Baseline (Day 1) to Days 15, 29, 43, and 57 on the difficulty subscale (total score on 9 items) of the FFI, ranging from 0 (“No Difficulty”) to 4 (“A Lot of Difficulty”) with EN3835 vs placebo.

 To assess the change in nodule size after administration of EN3835 vs placebo. 	
 The difference between EN3835 and placebo in the mean change from Baseline (Day 1) to Day 57 in the size of the treated nodules by caliper measurements. The mean change from Baseline (Day 1) to Days 15, 29, 43, and 57 in nodule size with EN3835 vs placebo.

Objective	Endpoint

• To assess the change in nodule consistency (by palpation) after administration of EN3835 vs placebo.	
• The difference between EN3835 and placebo in the change in consistency from Baseline (Day 1) to Day 57 as determined by the number of participants with a soft or non-palpable consistency at Day 57.• The change from Baseline (Day 1) to Days 15, 29, 43, and 57 in nodule consistency with EN3835 vs placebo.

^a. For use in this study, the Foot Function Index has been adapted for plantar fibromatosis (FFI-PF-May 2021), and will hereafter be referred to as FFI.

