4.6.2. Nodule Size by Caliper Measurement

Nodule size (ie, length and width) will be determined by handheld calipers and will be assessed for each treated nodule.

The size of nodule will be the larger of either nodule length or nodule width.

The area of nodule will be calculated as:

Area of the Nodule = (Nodule Width * Nodule Length * pi)/4 where pi=22/7

The nodule level data will be summarized by categories of nodule size, treatment group and visit. Only treated nodules will be included for data analyses and summarized at participant level. The change from Baseline (Day 1) in nodule size at EOS (Day 57) and other post baseline visits will be analyzed.

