4.6.3. Nodular Hardness by Durometer Assessment

Nodule hardness will be quantified using durometer and will be assessed for each treated nodule. The nodule level data will be summarized by treatment and visit, the change from Baseline (Day 1) in nodule hardness at EOS (Day 57) and other post baseline visits of the treatment will be analyzed. The average of all treated nodule hardness will be used for data analyses and summarization at participant level.

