6.2. Derived Variables

Table 25 defines the derived variables for study parameters:

Table 25: Derived Variables and Definition

Variable	Definition
Height (cm)	If height is recorded in inches, then height is equal to the recorded value multiplied by 2.54 and then rounded to 1 decimal place.
Weight (kg)	If weight is recorded in pounds, then weight is equal to the recorded value multiplied by 0.454 and then rounded to 1 decimal place.
Body Mass Index (BMI)	BMI will be computed using height measured at screening and body weight measured at respective visits as, $BMI (kg/m^2) = Weight (kg) / Height (m^2)$
Relative Day	The day of first injection of study intervention will be considered as relative Day 1.
Study Day	Study Day will be computed as, Date of Assessment – Date of Day 1 + 1 for assessment on or after Day 1, else study day will be computed as Date of Assessment – Date of Day 1.
Baseline	Baseline is defined as the last non-missing measurement/assessment prior to the first dose of study intervention. The assessments made in unscheduled visits will be considered in calculation of baseline, if the unscheduled assessment is the closest value preceding the study intervention injection.
Change from Baseline	Change from baseline will be derived as, post-baseline visit/time point value – the baseline value.
Last Date in Study	Last date in study is defined as: 
 • The date of EOS Visit (Day 57 ± 5), if the participant completes the study. • The date of early termination visits if the participant is terminated early from study at a non-scheduled visit. • The date of the latest scheduled visit if the participant is terminated early from study at a scheduled visit or lost to follow-up.
Duration (Days) of AE	AE end date - AE start date + 1
AE Onset Day	AE start date - Date of Day 1 + 1
Total Number of Nodules	Sum of all Nodules Identifier entered in Selected Nodule(s) form
Maximum of Nodule size (mm) (Caliper measurement) for participant level	Maximum of nodule size for the participant
Average Nodular Hardness (Durometer measurement) for Nodule level & Participant level	Average of nodule hardness
Area of the Nodule	$(Nodule\ Width * Nodule\ Length * \pi) / 4$ where $\pi = 22/7$
Area of Nodule for Participant level	Average of nodule area of all nodules

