7.6.4.7. Nodule Size by Caliper Measurement

7.6.4.7.1. Participant Level Analyses: Mean change from Baseline to Days 15, 29, 43 and 57 in the size of the treated nodules

The mean change from Baseline (Day 1) to Days 15, 29, 43, and 57 in the size of the treated nodules with EN3835 vs placebo and their treatment differences will be estimated using the similar statistical model based on observed data using MMRM (Section 7.6.1.3).

The LSM estimate for the mean change from baseline at each visit for each treatment group and the LSM for treatment difference at each visit and their 95% confidence interval (CI) will be presented.

The descriptive statistics for observed and change from baseline at each visit by treatment group will be provided. The nodule size (up to 2 cm, > 2 cm to ≤4 cm and > 4 cm) will also be summarized by each treated nodule.

A listing for nodule size will be provided by participant.

7.6.4.7.2. Nodule Level Analyses: Mean change from Baseline to Days 15, 29, 43 and 57 in the size of the treated nodules

Nodule level analyses will be performed on observed data using MMRM (Section 7.6.1.3).

The mean change in nodule size from baseline to Days 15, 29, 43, and 57 in EN3835 compared to placebo will be analyzed using a MMRM. An unstructured covariance matrix will be used to model the covariance of within-participant values. The Kenward-Roger approximation will be used to estimate denominator degrees of freedom. If the convergent criteria are not met then

other covariance matrix structure, ie., autoregressive (1) (AR (1)) will be used for model. The MMRM model will include:

- The dependent variable, the change from the Baseline to each visit (ie, change from baseline score to day 15, day 29, day 43, and day 57)
- The fixed effect, treatment group, study visit, treatment by visit interaction.
- The covariate, the baseline maximum of Nodule length/Nodule width for respective nodule at Day 1, maximum of Nodule length/Nodule width for respective nodule.
- The repeated measures will be the study visit and nodules.

The least square mean (LSM) estimate for each treatment at EOS, the LSM of treatment difference, their corresponding 95% confidence interval (CI) and associated p-value will be provided.

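### Exploratory nodule size: the SAP's only participant-level rule is the maximum over nodules, which can compare different nodules between visits and shift the estimate either way

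*SAP*

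**What the plan says.** Protocol Section 4 lists as exploratory the difference between arms in the "mean change from Baseline (Day 1) to Day 57 in the size of the treated nodules by caliper measurements". Protocol 10.3.1 has nodule-level data analysed at both levels, bases interpretation on the participant level, treats the nodule level as supportive, and leaves the mapping between them to the SAP.

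The SAP handles that mapping as follows:

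- **One nodule** (4.6.2): "The size of nodule will be the larger of either nodule length or nodule width".
- **Which nodules** (4.6.2): "Only treated nodules will be included for data analyses and summarized at participant level". No maximum, mean or sum is named. Table 26 cites this section as the participant-level derivation.
- **Participant-level size** (6.2, Table 25): "Maximum of nodule size for the participant". No visit is named and no index nodule is fixed.
- **Change** (6.2, Table 25): "Change from baseline will be derived as, post-baseline visit/time point value" minus the baseline value.
- **Analysis** (7.6.4.7.1): "The mean change from Baseline (Day 1) to Days 15, 29, 43, and 57 in the size of the treated nodules with EN3835 vs placebo", by MMRM on observed data, in the mITT population according to Table 27.
- **Hardness** (4.6.3), for contrast: "The average of all treated nodule hardness will be used for data analyses and summarization at participant level". Participant-level nodule area in Table 25 is also an average.

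The largest nodule dimension also appears as a covariate in the ANCOVA models (SAP 7.6.1.1).

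**The concern.** The endpoint concerns the treated nodules, in the plural. A maximum describes one nodule, and a difference of two maxima need not describe the same nodule twice. If the largest nodule shrinks below the second largest, the later value comes from the second and the change is cut short. If only a smaller nodule shrinks, the change is zero. If only the largest shrinks and stays largest, its full change is credited to the participant although the other nodules did not move.

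Eligibility allows up to three nodules in unilateral disease and two per foot in bilateral disease, so multi-nodule participants will occur; the documents do not give their share. At stake is whether the lead result for this endpoint measures what its wording promises, and whether it will agree with the area summary and the nodule-level analysis of the same caliper readings.

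**Working it through.** The plan gives no effect size, variance or nodule-count distribution for size, so there is no stated figure to reproduce. The sample size rests on the FFI pain endpoint and is not touched.

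**Step 1. Arithmetic on single records (mm).** Maximum rule = max(Day 57) − max(Day 1). Mean rule = average of each nodule's own change.

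| Day 1 | Day 57 | Maximum rule | Mean rule | Baseline-largest nodule |
|---|---|---|---|---|
| 22, 20 | 12, 20 | 20 − 22 = −2 | (−10 + 0)/2 = −5 | −10 |
| 30, 12 | 30, 2 | 30 − 30 = 0 | (0 − 10)/2 = −5 | 0 |
| 25, 15 | 15, 15 | 15 − 25 = −10 | (−10 + 0)/2 = −5 | −10 |
| 25, 20 | 20, 16 | 20 − 25 = −5 | (−5 − 4)/2 = −4.5 | −5 |

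The first row compares two different nodules. The second misses a 10 mm reduction. The third and fourth go the other way. With one nodule the rules coincide.

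**Step 2. Simulation of the mm effect.** All inputs are assumptions: true sizes uniform on 8-20 mm, caliper error SD 1.5 mm at each visit, no true change on placebo. Entries are the placebo-minus-active difference in mean change for 2 / 3 / 4 nodules.

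| Response on active | Maximum rule | Mean rule | Maximum relative to mean |
|---|---|---|---|
| Each nodule independently has a 50% chance of shrinking 40% | 2.56 / 2.31 / 2.08 | 2.81 / 2.80 / 2.81 | 9% / 18% / 26% smaller |
| Every nodule shrinks 3 mm | 3.00 / 3.00 / 3.00 | 3.00 / 3.00 / 3.00 | equal |
| All of a participant's nodules respond together (50% chance, 40%) | 3.15 / 3.34 / 3.44 | 2.79 / 2.81 / 2.80 | 13% / 19% / 23% larger |
| Only the largest nodule shrinks, by 40% | 3.72 / 2.89 / 2.36 | 3.20 / 2.26 / 1.76 | 16% / 28% / 34% larger |

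With other assumed sizes (mean 15 mm, SD 5) the direction is the same but the amounts differ: ratios of 0.98 / 0.93 / 0.88 for independent response and 1.17 / 1.26 / 1.32 for a uniform 20% shrinkage. If only the nodules that are not the largest shrink by 20%, the ratio falls to 0.09-0.11. In that set, caliper error alone changed which nodule was largest in 13-23% of placebo participants with two to four nodules.

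**Step 3. Precision.** Standardized effect = difference in mean change / pooled SD of change. For two independent nodules: 2.56/2.86 = 0.90 under the maximum, 2.81/2.11 = 1.33 under the mean. For 2 / 3 / 4 nodules, with about 0.01 variation between runs:

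- independent response: 0.90 / 0.84 / 0.80 against 1.33 / 1.62 / 1.87
- all respond together: 1.03 / 1.08 / 1.11 against 1.11 / 1.19 / 1.23
- every nodule shrinks 3 mm: 1.50 / 1.55 / 1.59 against 2.00 / 2.45 / 2.83
- only the largest shrinks, by 40%: 1.51 / 1.25 / 1.08 against 2.06 / 1.82 / 1.65

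The main reason is that averaging k nodules cuts the error SD of the change to 1.5·√(2/k), that is 1.50 / 1.22 / 1.06 mm. In the 3 mm scenario, where response does not vary, the SD under the maximum is 2.00 / 1.93 / 1.88 mm.

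One case reverses this. If only the largest nodule shrinks, and by 20% rather than 40%, the standardized effect is 1.14 / 1.04 / 0.94 under the maximum against 1.06 / 0.92 / 0.83 under the mean.

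**The case against.** **The per-visit maximum is inferred.** Table 25 names no visit, and its row may only define the covariate. This stands as a limit on the claim. But if the row is only the covariate, the SAP has no participant-level rule for the size endpoint, and the mapping that Protocol 10.3.1 leaves to the SAP is missing. Text is needed either way.

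**A reader might infer that the maximum understates the treatment effect.** The documents do not support that. SAP 7.6.4.7.1 reports least-squares mean differences, in mm, and Step 2 shows these can be smaller, equal or larger. Nothing in the documents says which pattern applies. Protocol 3.2.1 reports small caliper changes in both directions in the earlier Phase 1 study; this makes mixed response and measurement noise plausible but does not establish them, and the assumed 40% shrinkage is not drawn from it.

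**A reader might also infer that smaller nodules are ignored altogether.** They are not. The nodule-level MMRM (SAP 7.6.4.7.2) uses every treated nodule's own change, and average area per participant is defined. Because Protocol 10.3.1 makes the nodule level supportive, this reduces the problem without removing it.

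**The choice of summary is partly preference.** This is fair. Following the Day 1 largest nodule would also stop the switching, but it would still leave out the other treated nodules that the endpoint names.

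**Conclusion.** The point holds as a minor one. The participant-level rule for nodule size is incomplete, and on its natural reading it does not fit the endpoint: it can compare different nodules and gives no credit for shrinkage outside the largest. Relative to the mean change over treated nodules, the mm estimate can move either way: 9-26% smaller, equal, or 13-23% larger under independent, equal-mm and shared response. Precision is lower in every scenario examined in which all treated nodules can respond; the exception found is modest shrinkage confined to the largest nodule.

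The percentages rest on assumed sizes, shrinkage and caliper error, and apply only to participants with two or more nodules. The endpoint is exploratory with nominal p-values (SAP 6.5). The primary and key secondary endpoints, the sample size and the testing hierarchy do not depend on this change-score rule.

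**What to change.** In SAP 4.6.2 and Table 25, define participant-level nodule size at each visit as the average, over the nodules treated on Day 1, of the larger of length or width, and take change from the Day 1 average. This matches the hardness rule in 4.6.3. State that the set of nodules is fixed at Day 1 and how a treated nodule that can no longer be measured enters the average; dropping it would change the set again. Keep the Day 1 maximum as the model covariate and, if wanted, report the largest nodule as a descriptive line.

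The cost is SAP wording and minor programming on data already collected, and the lead result no longer describes the largest nodule. Settle it before unblinding, so that the choice among maximum, average and index nodule cannot follow the results.

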6.2.1. Derivation of Efficacy Parameter

Table 26 provides detailed information for the efficacy parameters as per eCRF/Vendor data collection. The derivation of these parameters is added on a participant-level, foot-level, and nodule-level.

Table 26: Efficacy Parameter Data

SN	Category	Parameter	Participant Level	Foot Level	Nodule Level	Derivation for Participant Level	Derivation for Foot Level	Derivation for Nodule Level
1	FFI	FFI Total Score	√			Section 4.7.1.4	NA	NA
2	FFI	FFI Pain Subscale Score	√			Section 4.7.1.4	NA	NA
3	FFI	FFI Difficulty Subscale Score	√			Section 4.7.1.4	NA	NA
4	FFI	FFI Pain & Difficulty combined score	√			Section 4.7.1.6	NA	NA
5	FFI	FFI Activity Limitation subscale score	√			Section 4.7.1.4	NA	NA
6	FFI	FFI Composite Score	√			Section 4.7.1.6	NA	NA
7	NRS	Pain intensity NRS	√			Section 4.7.4	NA	NA
8	Nodule	Nodule size by Caliper measurement	√		√	Section 4.6.2	NA	eCRF data
9	Nodule	Nodule Hardness by Durometer measurement	√		√	Section 4.6.3	NA	eCRF data
10	Nodule	Number of Nodules treated	√		√	Section 4.6.4	NA	eCRF data
11	Nodule	Nodular Consistency	√		√	Section 4.6.1	NA	eCRF data
12	PGIS	PGIS Overall Severity	√			Vendor data	NA	NA
13	PGIS	PGIS Pain Subscale	√			Vendor data	NA	NA
14	PGIS	PGIS Difficulty Subscale	√			Vendor data	NA	NA
15	PGIS	PGIS Activity Limitation subscale	√			Vendor data	NA	NA
16	PGIC	PGIC Overall Severity	√			Vendor data	NA	NA
17	PGIC	PGIC Pain Subscale	√			Vendor data	NA	NA
18	PGIC	PGIC Difficulty Subscale	√			Vendor data	NA	NA
19	PGIC	PGIC Activity Limitation Subscale	√			Vendor data	NA	NA
20	CGIC	Clinician Global Impression of Change Scale		√		Section 4.8.1	eCRF data	NA
21	SSTS	Subject Satisfaction with Treatment Scale		√		Section 4.8.1	eCRF data	NA

6.3. Handling of Missing Data

For categorical variables with missing values, a category documenting the frequency of missing values will be displayed in the summary tables. The participants having missing value for age, race/ethnicity, height, weight, nodule consistency status will be missing.

Immunogenicity samples with a positive titer value will undergo a log transformation for analyses. Samples with titer level < 10 will be assigned or imputed as a log transformed titer of 1 for analyses.

6.3.1. Handling of Missing Data for the Primary Endpoint

The foot pain subscale score will be recorded at baseline and at each visit (ie, Day 15, 29, 43, and 57).

The primary endpoint will be the change from baseline at Day 57. This value will be missing if the participants have missing data due to discontinuation from the study prior to Day 57 or due to a missed assessment or lost to follow up.

The missing data at Day 57 will be imputed for the participants who withdraw from the study prior to Day 57 using multiple imputation washout model (Section 7.6.1.2) to explore the possibility of data missing not at random (MNAR). In the multiple imputation washout framework, for participants who withdraw from the study early, their missing values will be

imputed under the assumption that their outcome would be similar to those in the placebo group with similar background characteristics. Multiple imputation methods will be used to account for uncertainty in the imputation process and results from the imputed datasets will be combined using Rubin's method.(4)

In addition, to assess the impact of missing values, sensitivity analyses using Mixed Model Repeated Measure (MMRM) (Section 7.6.1.3) without imputation and with imputation using Tipping Point Analyses (Section 7.6.1.2) will be performed on primary endpoint and key secondary endpoints. If the primary analyses of primary endpoint and key secondary endpoints result is not significant ($p\text{-value} > 0.05$), no sensitivity analyses (tipping point) will be performed.

6.3.2. Handling of Missing Data for Secondary and Exploratory Endpoints

Missing data at Day 57 for the key secondary endpoints of the FFI pain and difficulty combined score and nodular hardness, will be imputed using similar methods as described for primary efficacy endpoint. For the sensitivity analyses of the key secondary endpoint of the CGIC, missing data for CGIC will be imputed using the monotone logistic regression method (Section 7.6.3.2.2).

For other secondary endpoints and exploratory endpoints, missing data will not be imputed.

6.3.3. Missing Data Handling for Safety Data

There will be no imputation of missing values for safety data, however missing relationship between AE and study intervention will be considered as related to study intervention following worst case principle.

6.3.4. Imputation of Partial Dates

6.3.4.1. TEAE Status for Completely Unknown Start Date

The following rules will apply in cases where the start date of an AE is completely unknown:

- If the AE onset date is unknown and the end date is on or after study intervention injection on Day 1 or ongoing, then the AE will be considered a TEAE.
- If the AE onset date is unknown and the end date is before study intervention injection on Day 1, then the AE will not be considered a TEAE.
- If both the start and end dates are unknown (or end date is ongoing), then the AE will be considered a TEAE, following the worst-case principle.
- If the AE onset date is partly present and month/year is prior to the study intervention injection on Day 1, then the AE will not be considered a TEAE.

6.3.4.2. Concomitant Status of Medications with Completely Unknown Start Date

The following rules will apply in cases where the start date of a medication is completely unknown:

- If the medication onset date is unknown and the end date is after the date of after the study intervention is administered on Day 1 or the medication is ongoing at after

study intervention is administered on Day 1, then the medication will be considered as concomitant.

- If the medication onset date is unknown and the end date is before the date of study intervention administration on Day 1, then the medication will not be considered as concomitant.
- If both the start and end dates are unknown, then the medication will be considered as concomitant. This approach is the most conservative following the worst-case principle.
- If the medication onset date is partly present and month/year is prior to date of study intervention injection on Day 1 and medication/procedure is not ongoing at after study intervention injection on Day 1, then the medication will not be considered as concomitant.
- If the medication onset date is unknown and the end date is before the date of study intervention administration on Day 1, then the medication will not be considered as prior concomitant.

6.4. Subgroup Analyses

Exploratory subgroup analyses will be performed on the primary endpoint, key secondary endpoints, and frequency of TEAE. The subgroups are:

1. Number of injections (1 vs 2 vs 3 vs 4) at Day 1
2. Baseline FFI Total Pain Subscale Score: Group 1 vs Group 2
 - a. Group 1: FFI total pain subscale score ≤ 20 for participants without orthotics or FFI total pain subscale score ≤ 26 for participants with orthotics
 - b. Group 2: FFI total pain subscale score ≥ 21 for participants without orthotics or FFI total pain subscale score ≥ 27 for participants with orthotics

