The efficacy and safety of EN3835 was also demonstrated in participants with palmar Dupuytren's disease nodules. The results of the study suggested that single injections of EN3835 0.60 mg and EN3835 0.40 mg may be effective in the treatment of Dupuytren's disease nodules. Most AEs reported were local to the injection site and resolved within a median of 14 days.

Because EN3835 contains foreign proteins, severe allergic reactions can occur. Anaphylaxis was reported in a postmarketing clinical study in 1 patient who had previous exposure to EN3835 in the treatment of DC.

A detailed description of the chemistry, nonclinical and clinical pharmacology, efficacy, and safety of EN3835 is provided in the current edition of the IB of EN3835 for plantar fibromatosis.

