10.7. Subgroup Analysis

Analysis for primary endpoint, key secondary endpoints, and frequency of TEAEs will be performed in the following subgroups.

1. Number of injections (1 vs 2 vs 3 vs 4)
2. Baseline FFI pain subscale score: Group 1 vs Group 2
 - a. Group 1: subscale score ≤ 20 for participants without orthotics or subscale score ≤ 26 for participants with orthotics
 - b. Group 2: subscale score ≥ 21 for participants without orthotics or subscale score ≥ 27 for participants with orthotics

Subgroups maybe be combined with adjacent groups if the number of participants in that group is less than 10.

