3. STUDY DESIGN AND MEASURES

3.1. Study Design

This is a phase 2, double-blind, randomized, placebo-controlled study designed to assess the efficacy, safety and tolerability of EN3835 vs placebo in the treatment of plantar fibromatosis.

[figure not shown]
Participants will be screened to randomize approximately 172 participants into 2 groups, an EN3835 group (n ~86) and a placebo group (n ~86) in a 1:1 ratio. Study intervention will be administered intralesionally to all nodules present based on the size of each nodule at the doses described in the dosage table ([Table 4](#)). All nodules present on each foot on Day 1 must be treated. (If all nodules on each foot are not hard, firm throughout, moderately firm on Screening and Day 1, the participant will not be eligible for study inclusion). Nodules will be measured using calipers and the largest width or length will be used to determine the number of injections to be administered in each nodule. The total number of study intervention injections across all nodules present, shall not exceed 3 injections (1.35 mg) in a single foot when treating participants with unilateral plantar fibromatosis. When treating participants with bilateral plantar fibromatosis, the total number of study intervention injections across all nodules present shall not exceed 4 injections (1.8 mg) in total with each foot receiving a maximum dose of 0.9 mg. After receiving study intervention, participants will be encouraged to resume normal daily activities including walking and bearing weight on the treated foot/feet. All participants will return to the clinic for 4 follow-up visits, 2 weeks apart, on Days 15, 29, 43, and 57.

At the Day 29 visit, if the participant has any previously treated nodule(s) that remains palpable and measurable by caliper with a consistency of hard, firm throughout, moderately firm, or soft that is/are deemed appropriate for treatment by the investigator, and the Treatment 2 Criteria are met, a second dose of the study intervention may be administered.

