3.13. Adverse Events

All adverse events (AEs) and serious adverse events (SAEs) will be collected by the investigator from the time of signing the informed consent through the EOS Visit (Day 57), if eligible. This will include any AEs that are ongoing at the time of completion/termination of the study. Participants who request to discontinue from the study will be asked to complete the 28-day post treatment Safety Follow-up Visit (or phone call if a visit is not possible) to determine the status of any ongoing AEs/SAEs or the occurrence of any new AEs/SAEs.

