4.9.1.1. Treatment-Emergent Adverse Events

A TEAE is any condition that was not present prior to treatment with study intervention but appeared following treatment, was present at treatment initiation but worsened during treatment, or was present at treatment initiation but resolved and then reappeared while the individual was on treatment (regardless of the intensity of the AE when the treatment was initiated).

Refer to Section [6.3.4.1](#) to identify TEAE status when start date of an AE is unknown.

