7.6.5. Subgroup Analysis

The primary, key secondary, and frequency of TEAEs will be performed for the following subgroups:

1. Number of injections (1 vs 2 vs 3 vs 4) at Day 1

2. Baseline FFI Total Pain Subscale Score: Group 1 vs Group 2

- a. Group 1: FFI total pain subscale score ≤ 20 for participants without orthotics or FFI total pain subscale score ≤ 26 for participants with orthotics
- b. Group 2: FFI total pain subscale score ≥ 21 for participants without orthotics or FFI total pain subscale score ≥ 27 for participants with orthotics

Subgroups may be combined with adjacent groups (which have less number of participants until count of participant exceeds 10). if the number of participants in that group is less than 10.

The subgroup analyses will be tabulated similar to primary analyses for primary endpoint and key secondary endpoints (Section 7.6.1.2 for 1st and 3rd Key secondary endpoints and Section 7.6.3.2.1 for 2nd key secondary endpoint).

Incidence of TEAEs will be tabulated with risk difference and confidence interval using subgroups (Section 7.7.2).

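### TEAEs are pooled through Day 57, and no table named in SAP 7.7.2 separates events after the optional Day 29 treatment from events after the first treatment

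*SAP*

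**What the plan says.** SAP 6.4 puts TEAE frequency among the endpoints for exploratory subgroup analysis, and the first subgroup is "Number of injections (1 vs 2 vs 3 vs 4) at Day 1". SAP 7.6.5 repeats it and adds: "Incidence of TEAEs will be tabulated with risk difference and confidence interval using subgroups (Section 7.7.2". Protocol 10.7 has only "Number of injections (1 vs 2 vs 3 vs 4" and names no visit.

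On timing:
- SAP 3.13 collects adverse events "from the time of signing the informed consent through the EOS Visit (Day 57), if eligible".
- SAP 4.9.1.1 begins: "A TEAE is any condition that was not present prior to treatment with study intervention but appeared following treatment". Its other clauses also refer to the start of treatment. Nothing restarts or reattributes events at Day 29.
- SAP 3.1 provides that on Day 29, for previously treated nodules that are still palpable and measurable, and subject to the Treatment 2 criteria and the investigator's judgment, "a second dose of the study intervention may be administered".
- SAP 6.2, Table 25, derives AE onset day as "AE start date - Date of Day 1 + 1".

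SAP 7.7.2 names TEAE summaries by SOC and PT, severity, relationship, seriousness, special interest, death and duration. A participant enters once per SOC and PT. SAP 7.7.1 summarizes injection counts without event risk.

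**The concern.** The product is a foreign protein, and the protocol itself connects an allergic event with earlier exposure. Protocol 3.2 states: "Anaphylaxis was reported in a postmarketing clinical study in 1 patient who had previous exposure to EN3835 in the treatment of DC". Protocol 3.2.1 reports that on Day 57 of the EN3835-105 Retreatment Period all 10 participants tested had neutralizing AUX-I antibodies. That study was open-label with 24 participants. The present trial compares up to two treatments with placebo in about 172 participants, so it can describe tolerability at re-exposure against a control.

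The planned summaries do not use that opportunity. An event that follows the Day 29 injection falls in the row for the Day 1 injection count, beside events that follow the first treatment. If the same preferred term occurs after both treatments, the second occurrence adds nothing to incidence. What is at stake is whether the report can state the risk after a second treatment.

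**Working it through.** **1. Could any named output show the risk after the second treatment?**
- TEAE and AESI tables (SAP 7.7.2): pooled to Day 57. No.
- TEAEs by Day 1 injection count (SAP 7.6.5): pooled to Day 57. No.
- Exposure (SAP 7.7.1): injection counts only. No.
- Vital signs and foot examination (SAP 7.7.3 and 7.7.6): summarized by visit, but these are not TEAE risks.
- Participant listings (SAP 7.7.2): late events can be found, but without a denominator.

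**2. Denominator.** SAP 3.5 gives a difference of 5.0, SD 10, two-sided alpha 0.05, power 85% and 15% dropout. A two-sample t-test needs 72.8, so 73 per arm. 73 / 0.85 = 85.9, so 86 per arm and 172 in total. The plan's figure reproduces; 86 is used below as the active arm.

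**3. A rarer reaction that is more frequent on re-exposure (assumed risks).** Let p1 and p2 be the risks after doses 1 and 2, and f the share retreated. Take the two reactions as independent and ignore background events.

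Whole-study incidence = p1 + f(1 − p1)p2. The share first affected after Day 29 is f(1 − p1)p2 divided by that incidence. With p1 = 1% and p2 = 5%:

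| f | Whole-study incidence | First affected after Day 29 |
|---|---|---|
| 25% | 0.01 + 0.25 × 0.99 × 0.05 = 2.2% | 55% |
| 50% | 0.01 + 0.50 × 0.99 × 0.05 = 3.5% | 71% |
| 75% | 0.01 + 0.75 × 0.99 × 0.05 = 4.7% | 79% |

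A table restricted to retreated participants would have the expected value 5% in every row.

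**4. A common reaction and once-per-PT counting (assumed p1 = p2 = 30%, f = 50%).** Under independence:
- Whole-study incidence is 0.30 + 0.50 × 0.70 × 0.30 = 40.5%.
- 0.105 / 0.405 = 26% of affected participants are first affected after Day 29.
- 0.50 × 0.30 × 0.30 = 4.5% of the arm react to both doses and count once.

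If instead the same people react each time, incidence is 30%, exactly as if the second dose carried no risk, and 0.50 × 0.30 = 15% of the arm have a second reaction that does not show.

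**5. What zero events would support.** The one-sided 95% upper bound is 1 − 0.05^(1/m), with m the number retreated out of 86:

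| Share retreated | m | Upper bound |
|---|---|---|
| 25% | 22 | 12.7% |
| 50% | 43 | 6.7% |
| 75% | 64 | 4.6% |
| 90% | 77 | 3.8% |
| 100% | 86 | 3.4% |

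The whole-study denominator would suggest 3.4% in every case.

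**The case against.** The Day 1 count is a sound subgroup. It is set by nodule number and size before treatment, and naming Day 1 avoids grouping participants by a retreatment decision made after randomization. Nothing in the SAP says that later events are caused by the Day 1 dose. This stands, and the subgroup should be kept.

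A reader might infer that pooling distorts the dose contrast. For example, at an assumed 30% independent risk per injection, one visit gives 30% with 1 injection and 1 − 0.7^4 = 76% with 4, a ratio of 2.5. Through Day 57, with 80% of both rows retreated at the same count, the figures are 46.8% and 90.6%, a ratio of 1.9. But the SAP plans risk differences between EN3835 and placebo within each row, not a contrast of 4 with 1 injections. The difference between rows also barely moves (46 against 44 points), because the falling ratio is largely saturation.

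A reader might also infer that the comparison of arms is biased if retreatment rates differ. At 30% per treatment, 50% against 90% retreated gives 40.5% against 48.9%. Those shares are invented. Soft nodules also qualify for retreatment, so it may be common in both arms. In any case the randomized regimen is up to two treatments, and whole-study incidence is the risk of that regimen.

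Second-exposure safety is not unmonitored either. Severe hypersensitivity is an AESI with its own table and listing, anaphylaxis is reported as an SAE, and an unblinded DSMB convenes if at least 3% of participants have anaphylaxis. EN3835-105 reported no SAEs and no clinically relevant findings in antibody-positive participants, and the anaphylaxis case cited is a single patient. All this lowers the urgency. It does not supply an incidence with the right denominator.

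**Conclusion.** The point holds as a gap in safety reporting: from the summaries named in the SAP, risk after the second treatment cannot be estimated. The claim is limited to tables named in the SAP text. The shells are in SAP Module 2 and the DSMB outputs in its charter; neither was available, so a reader should not conclude that no such table exists anywhere.

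The size depends on the share retreated and on event risks, and the documents give neither. For retreatment of 25% to 75%, the assumed 5% second-dose risk would appear as 2.2% to 4.7%. If half were retreated without an event, the data would exclude risks above 6.7%, not 3.4%. No efficacy result and no whole-study safety comparison changes. The documents do not support calling the Day 1 subgroup wrong or the comparison of arms biased. The change is still worth making before database lock, because it is cheap and addresses a risk that the protocol itself raises.

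**What to change.** Keep the Day 1 subgroup and all pooled tables. Add to SAP 7.7.2 descriptive tables by arm for all TEAEs, AESIs, and injection-site and hypersensitivity events, counting each participant once per PT within each period:

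- **Period 1:** onset from the Day 1 injection to before the Day 29 injection, or before the Day 29 visit date if not retreated. The denominator is all dosed participants. Show it also by Day 1 injection count.
- **Period 2:** onset on or after the Day 29 injection. The denominator is retreated participants. Put later events in participants who were not retreated in a separate column, so that they are neither lost nor added to Period 1 follow-up.

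Each period then spans a nominal 28 days (Day 1 to 29 and Day 29 to 57). In Table 25, derive onset day from the most recent injection as well as from Day 1. Do not require the Day 29 injection count as a stratum: it depends on response and would split an already selected group. Footnote that retreated participants are a post-randomization subset, so Period 2 comparisons are descriptive.

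The cost is SAP wording, a period flag and a few tables from data already collected. SAP 6.3.4.1 refers only to the Day 1 injection, so a default is needed for events whose onset date is missing or falls on Day 29 with unclear order. The downside is wider uncertainty in Period 2, as the bounds in the working show.
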